9.3.2 Covariates

The following information will be extracted from MDV in this study.

Table 2. Definition of variables

Variable	Data extraction period	Details
Sex	Index date	Male/Female
Age	Index date	Age at Index date
Comorbidity and medical history	12 months before the index date (included)	
 - Coronary heart disease - Gastro-esophageal reflux disease - Obstructive sleep apnoea syndrome - Chronic obstructive pulmonary disease (COPD) - Lung cancer - Pulmonary hypertension 
See Annex 4 for code to define each comorbidity and medical history

Underlying disease (Pre-specified ILD)	12 months before the index date (included)	
 - Underlying Autoimmune Disease (Autoimmune ILD, Non-autoimmune ILD, Multiple, Unknown) - ILD Category (Hypersensitive pneumonitis, Exposure-related ILD, idiopathic nonspecific interstitial pneumonia (iNSIP), Unclassifiable idiopathic interstitial pneumonias (IIP), Sarcoidosis, RA-ILD, SSc-ILD, mixed connective tissue disease-ILD (MCTD-ILD), Other autoimmune ILD, Other ILD, Multiple, Unknown) - Pre-Specified ILD Clinical Diagnosis (Hypersensitive pneumonitis, Exposure-related ILD, iNSIP, Unclassifiable IIP, Sarcoidosis, RA-ILD, SSc-ILD, MCTD-ILD, Systemic Lupus Erythematosus-ILD (SLE-ILD), Polymyositis/Dermatomyositis-ILD (PM/DM-ILD), Sjogren ILD, Other autoimmune ILD, Other ILD, Multiple, Unknown) 
See Annex 5 for algorithm to define underlying diseases

Treatment	6 months before the index date (included) Follow-up period	
 - Rituximab - Tacrolimus - Mycophenolate - Cyclosporine - Cyclophosphamide - Azathioprine - Oral Corticosteroid - Tocilizumab - Nintedanib 
See Annex 3 for code to define each treatment
 
As for corticosteroid and immunosuppressive drugs during follow-up period, the same condition used for criteria of progression to PF-ILD will be applied.

Management	Follow-up period	
 - Oxygen therapy (HOT) - Lung transplant - Palliative care (oxygen inhalation, opioid use) 
See Annex 3 for code to define each management

Clinical examination	6 months before the index date (included)	
 - Pulmonary function test - HRCT/CT - KL-6 - SP-D 
See Annex 3 for code to define each clinical examination

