9.7.3 Subgroup analysis

The three subgroup analyses by underlying diseases defined by disease codes on the index date and 12-months lookback period as described in Annex 5 will be performed for patient background characteristics and treatment, primary outcome, and secondary outcomes.

<Subgroup Patterns>

Underlying Autoimmune Disease (Subgroup1): Autoimmune ILD, Non-autoimmune ILD, Multiple, Unknown

ILD Category (Subgroup 2): Hypersensitive pneumonitis, Exposure-related ILD, iNSIP, Unclassifiable IIP, Sarcoidosis, RA-ILD, SSc-ILD, MCTD-ILD, Other autoimmune ILD, Other ILD, Multiple, Unknown

Pre-Specified ILD Clinical Diagnosis (Subgroup 3): Hypersensitive pneumonitis, Exposure-related ILD, iNSIP, Unclassifiable IIP, Sarcoidosis, RA-ILD, SSc-ILD, MCTD-ILD, SLE-ILD, PM/DM-ILD, Sjogren ILD, Other autoimmune ILD, Other ILD, Multiple, Unknown

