ANNEX 5. ALGORITHMS FOR DEFINING UNDERLYING DISEASES

The following three subgroups will be defined to assess the distribution of underlying diseases and to perform subgroup analysis by underlying diseases.

Subgroup1: Autoimmune ILD, Non-autoimmune ILD, Multiple, Unknown, IPF[#]

Subgroup2: Hypersensitive pneumonitis, Exposure-related ILD, iNSIP, Unclassifiable IIP, Sarcoidosis, RA-ILD, SSc-ILD, MCTD-ILD, Other autoimmune ILD, Other ILD, Multiple, Unknown, IPF[#]

Subgroup3: Hypersensitive pneumonitis, Exposure-related ILD, iNSIP, Unclassifiable IIP, Sarcoidosis, RA-ILD, SSc-ILD, MCTD-ILD, SLE-ILD, PM/DM-ILD, Sjogren ILD, Other autoimmune ILD, Other ILD, Multiple, Unknown, IPF[#]

#Note: Patients grouped into IPF are excluded from study population according to the exclusion criteria.

The patients will be grouped according to the following three steps.

Step 1: Patients will be grouped based on the fibrosing-ILD code on the index date

If two or more different ⁽¹⁾ disease codes specified in this step 1 exist on index date, then subgroup1=subgrou2=subgrou3=Multiple

else if disease code on index date=8844510, then Subrgou1=Autoimmune ILD, subgroup2=SSc-ILD, subgroup3=SSc-ILD

else if disease code on index date=8847737, then subgroup1=Autoimmune ILD, subgroup2=RA-ILD, subgorup3=RA-ILD

else if disease code on index date=8848382, then subrgou1=Autoimmune ILD, subgroup2=Other autoimmune ILD, subgroup3=Other autoimmune ILD

else if disease code on index date=in(8848278, 8836513, 8844341), then subgroup1=Autoimmune ILD, subgroup2=Other autoimmune ILD. Subgroup3=SLE-ILD

else if disease code on index date=in(8848267, 8848302, 8839362, 8848283, 8837013), then subgroup1=Autoimmune ILD, subgroup2=Other autoimmune ILD, subgroup3=PM/DM ILD

else if disease code on index date=8834158, then subgroup1=Autoimmune ILD, subgroup2=Other autoimmune ILD, subgroup3=Sjogren ILD

(1)Note: The disease codes in the same conditional statement are NOT considered different. For example, disease codes of 8848278 and 8836513 are in the same conditional statement and these are not considered different disease codes. On the other hand, disease codes of 8848278 and 8848267 are in the different conditional statement and these are considered different disease codes.

Step 2: Patients not grouped in the step 1 will be grouped based on the earliest underlying disease code in the lookback period and fibrosing-ILD code on the index date

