else if two or more different ⁽²⁾ earliest underlying disease codes specified in this step 2 exist AND disease code on index date=in(J84.1, J84.9), then subgroup1=subgou2=subgrou3=Multiple

else if earliest underlying disease code=in(D86.0, D86.1, D86.3, D86.8, D86.9) AND disease code on index date=in(J84.1, J84.9), then subgroup1=Non-autoimmune ILD, subgroup2=Sarcoidosis, subgroup3=Sarcoidosis

else if earliest underlying disease code=in(J67.0, J67.1, J67.2, J67.3, J67.4, J67.5, J67.6, J67.7, J67.8, J67.9) AND disease code on index date=in(J84.1, J84.9), then subgroup1=Non-autoimmune ILD, subgroup2=Hypersensitive pneumonitis, subgroup3=Hypersensitive pneumonitis

else if earliest underlying disease code=J84.0 AND disease code on index date=in(J84.1, J84.9), then subgroup1=Non-autoimmune ILD, subgroup2=Other ILD, subgroup3=Other ILD

else if earliest underlying disease code=in(J60, J61, J62.8, J63.0, J63.1, J63.2, J63.3, J63.4, J63.5, J64, J65, J66.0, J66.1, J68.0, J68.4, J70.1, J70.3, J70.4, J70.8) AND disease code on index date=in(J84.1, J84.9), then subgroup1=Non-autoimmune ILD, subgroup2=Exposure-related ILD, subgroup3=Exposure-related ILD

Note: Disease codes of 8840951 and 8848245 are added to the coitional statement.

else if earliest underlying disease code=in(M05.0, M05.1, M05.2, M05.3, M05.8, M05.9, M06.0, M06.2, M06.3, M06.4, M06.8, M06.9) AND disease code on index date=in(J84.1, J84.9, 8840951, 8848245), **then** subgroup1=Autoimmune ILD, subgroup2=RA-ILD, subgroup3=RA-ILD

else if earliest underlying disease code=in(M32.1, M32.9) AND disease code on index date=in(J84.1, J84.9, 8840951, 8848245), **then** subgroup1=Autoimmune ILD, subgroup2=Other autoimmune ILD, subgroup3=SLE-ILD

else if earliest underlying disease code=in(M33.0, M33.1, M33.2, M33.9) AND disease code on index date=in(J84.1, J84.9, 8840951, 8848245), **then** subgroup1=Autoimmune ILD, subgroup2=Other autoimmune ILD, subgroup3= PM/DM ILD

else if earliest underlying disease code=in(M34.0, M34.1, M34.8, M34.9) AND disease code on index date=in(J84.1, J84.9, 8840951, 8848245), **then** subgroup1=Autoimmune ILD, subgroup2=SSc-ILD, subgroup3=SSc-ILD

else if earliest underlying disease code=M35.0 AND disease code on index date=in(J84.1, J84.9, 8840951, 8848245), **then** subgroup1=Autoimmune ILD, subgroup2=Other autoimmune ILD, subgroup3=Sjogren ILD

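### Annex 5 Step 2 labels patients by the earliest underlying-disease code in a 12-month lookback, so patients with the same two chronic diseases can be split between subgroups by visit timing

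*Combined protocol and SAP*

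**What the plan says.** Annex 5 assigns each patient a category in three subgroup schemes through a three-step chain. Step 1 uses disease-specific ILD codes on the index date. Step 2 takes those left over, who are "grouped based on the earliest underlying disease code in the lookback period", combined with the ILD code on the index date. Section 9.7.3 fixes the window, defining the subgroups by "disease codes on the index date and 12-months lookback period as described in Annex 5"; Table 2 in Section 9.3.2 also gives 12 months, with the index date included.

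The first branch of Step 2 assigns Multiple in all three schemes when two or more different "earliest underlying disease codes specified in this step 2 exist AND disease code on index date=in(J84.1, J84.9"). Note 2 explains that codes are different when they sit in different conditional statements. It says nothing about dates. The later autoimmune branches (RA, SLE, PM/DM, SSc, Sjögren, MCTD, other autoimmune) admit two further index codes, 8840951 and 8848245. The Multiple branch does not list these, and neither do the sarcoidosis, hypersensitivity pneumonitis, exposure-related and other-ILD branches.

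Under Section 9.7.3 the labels are used for background characteristics, the primary outcome and the secondary outcomes. No reason is given for choosing the earliest code, and the sensitivity analyses in Section 9.7.4 do not vary that choice.

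**The concern.** Section 7 sets out to describe incidence by co-existing underlying disease. If a disease was present before the window opened, its first code inside the window shows when a visit fell. It does not show which disease came first or which one underlies the ILD. The plan accepts that code dates follow visit schedules: Section 9.7.4 justifies the alternative index date by patients who may attend only annually.

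A patient with RA and sarcoidosis could therefore be labelled RA-ILD, Sarcoidosis or Multiple according to appointment order, and could fall on either side of the autoimmune line. Subgroup incidence curves would then mix patients with the same disease pair, and membership of Multiple would partly reflect whether both diseases are coded at one visit. The label can also move within the plan: the analysis that shifts the index date to the first ILD code shifts the lookback with it, so a patient with two prevalent diseases may change subgroup for that reason alone.

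**Working it through.** The plan states no figure to reproduce. From the documents I take the Step 2 chain, its Multiple branch, the 12-month window and the admitted index codes. The following are assumptions: both diseases are prevalent when the window opens, each is coded at every visit to its own clinic, visits are independent, the intervals are as shown, and the index-date ILD code is not itself the earliest underlying-disease code.

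**Formulas.** Let the first in-window visit fall uniformly on days 1 to m for one disease and 1 to n for the other, with m ≤ n.

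- Same earliest date: 1/n
- Less often seen disease first: (m − 1)/(2n)
- More often seen disease first: the remainder

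**Same-date reading, index code J84.1 or J84.9**

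| Intervals (days) | First disease | Second disease | Multiple |
|---|---|---|---|
| 28 / 28 | 27/56 = 48.2% | 48.2% | 1/28 = 3.6% |
| 56 / 56 | 55/112 = 49.1% | 49.1% | 1/56 = 1.8% |
| 84 / 84 | 83/168 = 49.4% | 49.4% | 1/84 = 1.2% |
| 28 / 84 | 82.7% | 27/168 = 16.1% | 1/84 = 1.2% |

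Simulating the Step 2 chain for RA plus sarcoidosis, 100,000 patients per scenario, gave the same pattern: 48.4 / 48.3 / 3.3% at 30/30 days, 49.6 / 49.2 / 1.1% at 90/90 and 82.8 / 16.0 / 1.2% at 30/90.

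**Some patients coded for both diseases on one date.** If a share s has same-date coding and intervals are equal, Multiple = s + (1 − s)/n.

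- s = 0.3: 0.3 + 0.7/84 = 30.8% to 0.3 + 0.7/28 = 32.5%; each single label about 34–35%
- s = 0.7: 0.7 + 0.3/84 = 70.4% to 0.7 + 0.3/28 = 71.1%; each single label about 14–15%
- s = 1: all Multiple

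**Any-date reading, index code J84.1 or J84.9.** Two different codes anywhere in the lookback give Multiple. Every patient with two diseases gets that label, and there is no split.

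**Index code 8840951 or 8848245 as the only ILD code on the index date, either reading.** The Multiple branch cannot apply, so the chain goes on to the earliest code.

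- RA plus Sjögren: ties go to RA because its branch comes first. Equal 28-day visits give 48.2 + 3.6 = 51.8% RA-ILD and 48.2% Sjögren ILD; equal 84-day visits give 50.6% and 49.4%. With RA every 28 days and Sjögren every 84, the split is 82.7 + 1.2 = 83.9% and 16.1%.
- RA plus sarcoidosis: patients with sarcoidosis coded first (48.2–49.4% at equal intervals) match no Step 2 branch, because the sarcoidosis branch requires J84.1 or J84.9. They pass to Step 3 and become Other autoimmune ILD.

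**The case against.** The strongest reply is that Note 2 defines different codes without mentioning dates. If any two classes in the lookback suffice, most of the problem disappears. That is true for J84.1 and J84.9. However, the word earliest would then do no work in that branch, two programmers could implement it differently, and the other two index codes are still not covered.

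Several stronger readings are tempting but unsupported:

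- A reader might infer that Step 2 is stricter than Steps 1 and 3 about a second disease. Those steps also examine a single date, the index date.
- A reader might infer that coding both diseases at one visit always yields Multiple. With index code 8840951 or 8848245 it does not.
- A reader might call the split purely arbitrary. It favours the disease seen more often, and for a disease first diagnosed inside the window the order can be real.
- A reader might infer damage to every subgroup contrast. Step 1 patients are untouched. Two autoimmune diseases coded on different dates both stay Autoimmune ILD in Subgroup 1, and SLE, PM/DM and Sjögren share one category in Subgroup 2. Crossing the autoimmune line needs an autoimmune plus non-autoimmune pair.
- A reader might want the rule replaced outright. Because Annex 5 sets Multiple in all three schemes at once, a plain all-codes rule would take RA plus Sjögren patients out of Autoimmune ILD in Subgroup 1, where they belong.

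It is also fair that the subgroup analyses are descriptive, with no between-subgroup test planned, and that the visit patterns above are assumed.

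**Conclusion.** The concern holds for patients labelled in Step 2 who have two or more underlying-disease classes in the lookback. For index codes J84.1 and J84.9 it depends on the same-date reading, which is the more natural one but is not stated. For 8840951 and 8848245 it holds on either reading. Among such patients the split can range from nearly even to about 83/16, and Multiple from about 1% to 100%, depending on visit frequency and same-date coding.

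How many patients this concerns is not given, so neither a large nor a slight effect on the subgroup results can be claimed. The overall primary estimate is not affected by the split: the same chain drives the IPF exclusion, but only in Step 3 and only when no other fibrosing-ILD code is present on the index date. The change is worth making because subgroup incidence is a stated purpose of the study and no planned analysis would reveal the dependence.

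**What to change.** 1. In Annex 5 Step 2, apply one Multiple rule to all four admitted index codes (J84.1, J84.9, 8840951, 8848245), and state whether it requires the different codes to share the earliest date.
2. The current label may stay as the main one. Add a sensitivity analysis that repeats the primary-outcome subgroup tables with a label based on all underlying-disease codes in the 12-month lookback, and cross-tabulate the two labels.
3. In that analysis, assign Multiple separately within each scheme, only when the codes map to different categories of that scheme. RA plus Sjögren would then remain Autoimmune ILD in Subgroup 1 and become Multiple in Subgroups 2 and 3. Do not count 8848245 by itself as a second disease: Step 2 lists it both as an admitted index code and as an underlying-disease code, so RA with 8848245 would otherwise become Multiple automatically.

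The cost is some wording in Annex 5, a little more programming and one extra set of tables, with no new data. Multiple will be larger in the sensitivity tables and the single-disease groups smaller, by an amount not known in advance. The cross-tabulation will show it.

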7. RATIONALE AND BACKGROUND

The term interstitial lung disease (ILD) encompasses a large group of over 200 pulmonary disorders. While idiopathic pulmonary fibrosis (IPF) is the best-known progressive fibrosing ILD (PF-ILD), there is a group of patients with different underlying clinical ILD diagnoses other than IPF who develop a progressive fibrosing phenotype during the course of their disease (e.g., idiopathic interstitial pneumonias [IIPs] such as idiopathic nonspecific interstitial pneumonia [iNSIP] and unclassifiable IIP; hypersensitivity pneumonitis [HP]; autoimmune interstitial lung disease [connective tissue disease-ILDs (CTD-ILD) such as rheumatoid arthritis-ILD (RA-ILD), systemic sclerosis-ILD (SSc-ILD) and anti-synthetase syndrome]; Sarcoidosis; Pneumoconiosis/exposure related ILD) [P17-10582, P18-04729, P19-01738, R19-0854]. These patients demonstrate a number of similarities to patients with IPF, with their disease being defined by the presence of progressive pulmonary fibrosis, worsening respiratory symptoms, declining lung function despite immunomodulatory therapies and, ultimately, early mortality.

Although there had been no indicated therapies for patients with chronic fibrosing ILDs with a progressive phenotype (other than IPF), Nintedanib has just been approved for SSc-ILD in the end of Dec. 2019 based on the results of the SENSCIS trial (NCT02597933) [P19-04387] and for PF-ILDs in the end of May 2020 in Japan based on the results of the INBUILD trial (NCT02999178) [P19-08802, P20-02333].

There is minimal literature available to estimate the proportion of patients who develop PF-ILDs in patients with fibrosing ILD other than IPF in Japan. In addition, the current management and treatment for these diseases are not well-known. These information are keys to gaining a better understanding of the size of this population with high unmet need and for physicians, patients and other stakeholders to optimize allocation of resources, diagnostic assessment and management of this patient population.

Therefore, this study will use the database from Medical Data Vision (MDV) to investigate the incidence probability of progression to PF-ILDs according to each co-existing underlying diseases and the characteristics of procedures for management and treatment in patients with fibrosing ILD other than IPF.

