else if earliest underlying disease code=7109008 AND disease code on index date=in(J84.1, J84.9, 8840951, 8848245), **then** subgroup1=Autoimmune ILD, subgroup2=MCTD-ILD, subgroup3=MCTD-ILD

else if earliest underlying disease code=in(8841317, 8850417, 8848245, M35.2, M35.3, M35.4, M35.5, M35.6, M35.7, M35.8, M35.9, M30.0, M30.1, M30.2, M30.3, M30.8, M31.0, M31.1, M31.2, M31.3, M31.4, M31.6, M31.7, M31.8, M31.9) AND disease code on index date=in(J84.1, J84.9, 8840951, 8848245), **then** subgroup1= Autoimmune ILD, subgroup2=Other autoimmune ILD, subgroup3=Other autoimmune ILD

(2)Note: The earliest underlying disease codes in the same conditional statement are NOT considered different. For example, earliest underlying disease codes of D86.0 and D86.1 are in the same conditional statement and these are not considered different earliest underlying disease codes. On the other hand, earliest underlying disease codes of D86.0 and J67.0 are in the different conditional statement and these are considered different earliest underlying disease codes.

Step 3: Patients not grouped in the step 1 and 2 will be grouped based on the fibrosing-ILD code on the index date

else if disease code on index date=in(5163005, 5150011, 8849927) AND no other fibrosing-ILD code on the index date, **then** subgroup1=subgroup2=subgroup3=IPF. These patients will be excluded from study population.

else if two or more different ⁽³⁾ disease codes including disease code of IPF specified in this step 3 exist on index date, **then** subgroup1=subgorup2=subgrou3=Multiple

else if disease code on index date=in(8850547, 8845727), **then** subgroup1=Non-autoimmune ILD, subgroup2=iNSIP, subgroup3=iNSIP

else if disease code on index date=in(5168008, 5168009, 5150001, 8845731, 8845640, J84.9), **then** subgroup1=Non-autoimmune ILD, subgroup2=Unclassifiable IIP, subgroup3=Unclassifiable IIP

else if disease code on index date=in(1363003, 8845663, 8845714, 8845719, 5168010), **then** subgroup1=Non-autoimmune ILD, subgroup2=Other ILD, subgroup3=Other ILD

else if disease code on index date=in(8840951, 8848245), **then** subgroup1=Autoimmune ILD, subgroup2=Other autoimmune ILD, subgroup3=Other autoimmune ILD

else subgroup1=subgroup2=subgroup3=Unknown

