desquamative interstitial pneumonia	J841	8845719	Non-autoimmune	Other IIPs	Other IIPs
lymphocytic interstitial pneumonia	J841	5168010	Non-autoimmune	Other IIPs	Other IIPs
-	-	-	Non-autoimmune	Unclassifiable	Unclassifiable
interstitial pneumonia	J849	4860015	Non-autoimmune	Unclassifiable	Unclassifiable
interstitial lung disease	J849	5168003	Non-autoimmune	Unclassifiable	Unclassifiable
respiratory disorder in dermatosclerosis	M348	8844510		SSc-ILD	SSc-ILD
respiratory disorder complicated by granulomatosis with polyangiitis	M313	8848382		other CTD-ILD	other CTD-ILD
lupus pneumonia	M321	8844341		SLE-ILD	SLE-ILD

systemic lupus erythematosus interstitial pneumonia	M321	8848278		SLE-ILD	SLE-ILD
respiratory disorder in systemic lupus erythematosus	M321	8836513		SLE-ILD	SLE-ILD
interstitial pneumonia in juvenile dermatomyositis	M330	8848267		PM/DM-ILD	PM/DM-ILD
interstitial pneumonia in dermatomyositis	M331	8848302		PM/DM-ILD	PM/DM-ILD
respiratory disorder in dermatomyositis	M331	8839362		PM/DM-ILD	PM/DM-ILD
interstitial pneumonia in polymyositis	M332	8848283		PM/DM-ILD	PM/DM-ILD
respiratory disorder in polymyositis	M332	8837013		PM/DM-ILD	PM/DM-ILD
respiratory disorder in Sjogren's syndrome	M350	8834158		Sjogren-ILD	Sjogren-ILD
interstitial pneumonia due to collagen disease	M351	8848245		other CTD-ILD	other CTD-ILD
rheumatoid lung disease	M0510	8840951		other CTD-ILD	
rheumatoid arthritis interstitial pneumonia	M0510	8847737		RA-ILD	RA-ILD

N-Total number of study patients in each ILD underlying autoimmune disease category, IPF – Idiopathic Pulmonary Fibrosis, iNSIP – Idiopathic Nonspecific Interstitial Pneumonia, IIP – Idiopathic Interstitial Pneumonia, SSc-ILD – Systemic Sclerosis- Associated ILD, RA-ILD – Rheumatoid-Associated ILD, SLE-ILD – Systemic Lupus Erythematosus ILD, PM/DM ILD – Polymyositis/Dermatomyositis ILD

Disease	ICD-10 Code	billing code	Linkage Fibrotic code	Underlying Autoimmune Disease	ILD Category	Pre-Specified ILD Clinical Diagnosis
Sjogren's syndrome	M350	7102001	J84.1, J84.8, J84.9, J99.0, J99.1	Autoimmune	Other-autoimmune/CTD ILD	Sjogren ILD
Sjogren's syndrome myopathy	M350	8841440	J84.1, J84.8, J84.9, J99.0, J99.1	Autoimmune	Other-autoimmune/CTD ILD	Sjogren ILD
respiratory disorder in Sjogren's syndrome	M350	8834158	J84.1, J84.8, J84.9, J99.0, J99.1	Autoimmune	Other-autoimmune/CTD ILD	Sjogren ILD
primary Sjogren's syndrome	M350	8848230	J84.1, J84.8, J84.9, J99.0, J99.1	Autoimmune	Other-autoimmune/CTD ILD	Sjogren ILD

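### Annex 5, Step 2: index codes 8840951 and 8848245 were added to the autoimmune branches but not to the Multiple rule, so some ties are settled by list order; code 8840951 also lacks a single destination

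*Combined protocol and SAP*

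**What the plan says.** Section 7 gives as a purpose the incidence of progression "according to each co-existing underlying diseases". Section 9.7.3 applies the Annex 5 groups to background characteristics, the primary outcome and the secondary outcomes, and section 9.7.4 repeats all analyses in sensitivity runs.

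Annex 5 works in three steps, each a chain of conditions in which the first match decides.

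- **Step 1** uses specific index codes. Among them, 8847737 leads to RA-ILD.
- **Step 2** combines the earliest underlying disease code with the index code. It opens with the rule for two or more different earliest codes: "AND disease code on index date=in(J84.1, J84.9), then subgroup1=subgou2=subgrou3=Multiple". Four non-autoimmune branches follow, with the same two index codes. Then comes a note, "Note: Disease codes of 8840951 and 8848245 are added to the coitional statement", and seven autoimmune branches whose index condition reads "AND disease code on index date=in(J84.1, J84.9, 8840951, 8848245" and so on. The first of these is the rheumatoid arthritis branch, "else if earliest underlying disease code=in(M05.0, M05.1, M05.2, M05.3, M05.8, M05.9" and further M06 codes, which leads to RA-ILD.
- **Step 3** takes whoever is left. The branch "else if disease code on index date=in(8840951, 8848245" leads to Autoimmune ILD in scheme 1 and Other autoimmune ILD in schemes 2 and 3.

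Annex 6 lists 8840951 as "rheumatoid lung disease", ICD-10 M0510, in the category other CTD-ILD. It lists 8847737, with the same ICD-10 code, as RA-ILD.

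**The concern.** Two index codes were added to part of Step 2 only. The branches that assign a single autoimmune disease accept them; the rule that recognises two competing diseases does not. The same pair of underlying diseases can therefore receive a different label depending on which fibrosing-ILD code was recorded on the index date, and between two autoimmune diseases the order of the list decides. The plan gives no reason for that order.

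The second issue is 8840951. Its ICD-10 code leads to RA-ILD by two routes and to Other autoimmune ILD by a third. Which route applies depends on two matters that the plan does not settle: whether codes are matched by ICD-10 or by billing code, and whether the index-date record counts as an underlying code. Two careful programmers could place the same patient differently, and the second-person check in section 9.8 cannot resolve an unclear specification.

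At stake are the subgroup tables and Kaplan-Meier curves, above all those for RA-ILD, Other autoimmune ILD and Multiple.

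**Working it through.** The plan states no figure on this point, so there is none to reproduce. The check applies Steps 2 and 3 literally.

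**Number of possible ties.** Step 2 has 11 branches: 4 non-autoimmune (sarcoidosis, hypersensitivity pneumonitis, J84.0, exposure-related) and 7 autoimmune (RA, SLE, PM/DM, SSc, Sjogren, MCTD, other autoimmune). Note (2) in Annex 5 treats codes from different branches as different. Pairs of different branches:

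- all: 11 × 10 / 2 = 55
- both autoimmune: 7 × 6 / 2 = 21
- one of each: 4 × 7 = 28
- both non-autoimmune: 4 × 3 / 2 = 6
- check: 21 + 28 + 6 = 55

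**Result as written.**

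| Tied pair | Index code J84.1 | Index code 8840951 or 8848245 alone |
|---|---|---|
| Both autoimmune (21) | Multiple, 21 of 21 | Branch listed first, 21 of 21 |
| Mixed (28) | Multiple, 28 of 28 | The autoimmune disease, 28 of 28 |
| Both non-autoimmune (6) | Multiple, 6 of 6 | Step 3, Other autoimmune ILD, 6 of 6 (if the index code is not itself an underlying code) |

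**Where the 21 autoimmune pairs go.** By list order, RA takes 6 pairs, SLE 5, PM/DM 4, SSc 3, Sjogren 2 and MCTD 1, total 21. In scheme 2, SLE, PM/DM and Sjogren all belong to Other autoimmune ILD. The split is therefore RA-ILD 6, Other autoimmune ILD 5 + 4 + 2 = 11, SSc-ILD 3 and MCTD-ILD 1. In scheme 1 all 21 become Autoimmune ILD instead of Multiple. These are counts of disease combinations, not of patients.

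**Example.** RA and SSc tied as earliest: with J84.1, Multiple in all three schemes; with 8840951 alone, Autoimmune ILD, RA-ILD and RA-ILD. If J84.1 or J84.9 is also coded on the index date, the Multiple rule applies after all.

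**Routes for M0510.**

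| Place | Code | Destination (schemes 2 and 3) |
|---|---|---|
| Step 1 | Index code 8847737 (M0510) | RA-ILD |
| Step 2 | Underlying code M05.1 with index code 8840951 | RA-ILD |
| Step 3 | Index code 8840951, not placed earlier | Other autoimmune ILD |
| Annex 6 | 8840951 (M0510) | other CTD-ILD |

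Take a patient with 8840951 on the index date and no other underlying code. If M0510 is matched to M05.1 and the index date is searched, Step 2 gives RA-ILD. If not, Step 3 gives Other autoimmune ILD. Table 2 and section 9.7.3 include the index date in the search; Step 2 mentions only the lookback period. Annex 5 mixes ICD-10 and seven-digit codes in its conditions without saying at which level a record is matched. Scheme 1 is Autoimmune ILD either way.

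**Overall estimate.** The IPF group requires that no other fibrosing-ILD code stand on the index date. A patient with 8840951 or 8848245 on that date cannot be in it. Neither issue changes who is in the cohort, so the overall Kaplan-Meier estimate is the same.

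**The case against.** The strongest reply is that the omission may be intended. Both added codes are themselves autoimmune ILD codes, they are also absent from all four non-autoimmune branches, and a note marks where they were added. For a mixed pair such as sarcoidosis and RA, letting an autoimmune index code decide is coherent. This stands, and the point is not pressed for mixed or non-autoimmune pairs. It does not explain ties between two autoimmune diseases, where the index code gives no ground for preferring the branch listed first.

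The case is also narrow. It needs two different codes that are both earliest, in effect on the same date, and no J84.1 or J84.9 on the index date. That stands and limits the size.

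On 8840951, a reader might infer that the plan puts rheumatoid lung disease in the wrong subgroup. The documents do not support that. Step 3 is a fallback for patients whom Steps 1 and 2 did not place, and it agrees with the Annex 6 category. Patients with 8840951 and an RA code as earliest underlying code have already gone to RA-ILD. What remains is an inconsistency between routes and an unstated matching level. The last Annex 6 column is blank for this code, but text extraction may be the cause, so nothing rests on it.

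A reader might also infer that RA-ILD absorbs the overlap patients in general. It takes only pairs that include RA, 6 of 21; in scheme 2 more pairs (11) go to Other autoimmune ILD.

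**Conclusion.** The point holds in a limited form. Followed as written, Step 2 labels a tie between two autoimmune diseases as Multiple for index codes J84.1 and J84.9, and by list order for 8840951 or 8848245 alone. This affects all 21 autoimmune pairs and all three subgroup schemes. The routing of 8840951 is inconsistent and affects schemes 2 and 3 only.

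The size in patients cannot be computed, because the documents give no code frequencies; given the conditions for a tie it is probably small. A bias in percentage points would require assuming both the share of patients moved and the difference in progression between groups, and nothing in the documents supports a value for either. It would be wrong to conclude that the autoimmune subgroup results are materially biased, or that the overall primary estimate is affected. This is a minor correction to the specification. The conclusion rests on reading each step as an ordered chain, as its else-if form implies.

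**What to change.** In Annex 5 and Annex 6:

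- Extend the Step 2 Multiple condition to index codes 8840951 and 8848245 for ties between different autoimmune branches. Do not count the index-date 8840951 or 8848245 record itself as the second disease; 8848245 is also listed as an underlying code in the last Step 2 branch, so without this it could create a tie with itself. All 21 autoimmune pairs then go to Multiple whichever index code is present. The other 28 + 6 = 34 pairs stay as they are; a sentence should say that this is intended.
- Give 8840951 one destination across Steps 2 and 3 and Annex 6. RA-ILD would match its ICD-10 code and the treatment of 8847737; if Other autoimmune ILD is preferred, say why and make Step 2 agree.
- State whether matching is by ICD-10 or by billing code, including whether M0510 counts as M05.1, and whether the index-date code counts as an underlying code.

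The cost is a few lines of text and the matching lines of program. No new data are needed, and probably few patients change group.
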